**Table 9: Solicited Adverse Reactions and Grades: Age 6 Months to ≤ 36 Months**

Reaction	Grade 0	Grade 1	Grade 2	Grade 3	Grade 4 
Local Reaction					
Injection site pain/tenderness	None	Mild discomfort to touch or some pain but no interference with normal daily activities	Cries when limb is moved/refuses to move limb or pain interferes with normal daily activities	Significant pain at rest or pain prevents normal daily activities	Requires emergency room visit  or hospitalization
Injection site erythema (redness)	< 5 mm/ < 0.5 cm	5-20 mm/ 0.5-2.0 cm	> 20-50 mm > 2.0-5.0 cm	> 50 mm/ > 5 cm	Necrosis or exfoliative dermatitis
Injection site swelling/induration (hardness)	< 5 mm/ < 0.5 cm	5-20 mm/ 0.5-2.0 cm	> 20-50 mm > 2.0-5.0 cm	> 50 mm/ > 5 cm	Necrosis

Reaction	Grade 0	Grade 1	Grade 2	Grade 3	Grade 4 
Groin or underarm swelling or tenderness ipsilateral to the side of injection	None	Some swelling or tenderness but no interference with normal daily activities	Swelling or tenderness that interferes with normal daily activities	Swelling or tenderness that prevents normal daily activities	Emergency room visit  or hospitalization
Systemic Reaction					
Fever	< 38.0°C	38.0-38.4°C 100.4-101.1°F	38.5-39.5°C 101.2-103.1°F	39.6-40.0°C 103.2-104.0°F	> 40.0°C > 104.0°F
Irritability/crying	None	Lasting < 1 hour or easily consolable	Lasting 1-3 hours or requiring increased attention	Lasting > 3 hours or inconsolable	Requires emergency room visit  or hospitalization
Sleepiness	None	Sleepier than usual or less interested in surroundings	Not interested in surroundings or sleeps through meals	Sleeps most of the time, hard to arouse	Inability to arouse
Loss of appetite	None	Eating less than normal for 1-2 feeds/meals	Missed 1-2 feeds/ meals completely	Missed > 2 feeds/meals completely or refuses most feeds/meals	Requires emergency room visit  or hospitalization

 Age at time of enrollment determines the scale to be used.

 Grading for Grade 4 events per investigator assessment (with exception of fever).

 Emergency room visit includes urgent care visit.

Source: Guidance for industry – Toxicity Grading Scale for Healthy Adult and Adolescent Volunteers Enrolled in Preventative Vaccine Clinical Trials ([DHHS 2007](#)).

Any solicited AR that meets any of the following criteria must be entered into the participant's source document and must also be recorded by the study site staff on the solicited AR page of the participant's eCRF:

- Solicited local or systemic AR that results in a visit to a healthcare practitioner (HCP; otherwise meets the definition of an MAAE)
- Solicited local or systemic AR leading to the participant withdrawing from the study or the participant being withdrawn from the study by the investigator (AE leading to withdrawal)
- Solicited local or systemic AR lasting beyond 7 days after injection
- Solicited local or systemic AR that leads to participant withdrawal from IP

- Solicited local or systemic AR that otherwise meets the definition of an SAE

#### 7.4.4 Medically Attended Adverse Events

An MAAE is an AE that leads to an unscheduled visit to an HCP. This would include visits to a study site for unscheduled assessments (eg, abnormal laboratory test result follow-up, COVID-19 [[Section 7.3.1](#)]) and visits to HCPs external to the study site (eg, urgent care, primary care physician). Investigators will review unsolicited AEs for the occurrence of any MAAE. Unsolicited AEs will be captured on the AE page of the eCRF.

While COVID-19 surveillance is ongoing, all confirmed symptomatic COVID-19 cases ([Section 7.3.1](#)) will be recorded as MAAEs. Any severe COVID-19 cases will be reported to the Sponsor or designee immediately and in all circumstances within 24 hours, using the SAE Mailbox, the SAE Hotline, or the SAE Fax line ([Section 7.4.11](#)). The investigator will submit any updated COVID-19 case data to the Sponsor within 24 hours of it being available.

Once COVID-19 surveillance is discontinued, COVID-19 related AEs will be reported per standard AE reporting for the respective SoA.

All suspected cases of anaphylaxis should be recorded as MAAEs and reported as an SAE, based on criteria for a medically important event, unless the event meets other serious criteria. As an SAE, the event should be reported to the Sponsor or designee immediately and in all circumstances within 24 hours as per [Section 7.4.11](#). The investigator will submit any updated anaphylaxis case data to the Sponsor within 24 hours of it being available. For reporting purposes, a participant who displays signs/symptoms consistent with anaphylaxis as described below should be reported as a potential case of anaphylaxis. This is provided as general guidance for investigators and is based on the Brighton Collaboration case definition ([Rüggeberg et al 2007](#)).

Anaphylaxis is an acute hypersensitivity reaction with multi-organ-system involvement that can present as, or rapidly progress to, a severe life-threatening reaction. It may occur following exposure to allergens from a variety of sources.

Anaphylaxis is a clinical syndrome characterized by:

Sudden onset AND

Rapid progression of signs and symptoms AND

Involves 2 or more organ systems, as follows:

- **Skin/mucosal:** urticaria (hives), generalized erythema, angioedema, generalized pruritus with skin rash, generalized prickle sensation, red and itchy eyes

- **Cardiovascular:** measured hypotension, clinical diagnosis of uncompensated shock, loss of consciousness or decreased level of consciousness, evidence of reduced peripheral circulation
- **Respiratory:** bilateral wheeze (bronchospasm), difficulty breathing, stridor, upper airway swelling (lip, tongue, throat, uvula, or larynx), respiratory distress, persistent dry cough, hoarse voice, sensation of throat closure, sneezing, rhinorrhea
- **Gastrointestinal:** diarrhea, abdominal pain, nausea, vomiting

#### 7.4.5 Adverse Events of Special Interest

An AESI is an AE (serious or nonserious) of scientific and medical concern specific to the Sponsor's product or program for which ongoing monitoring and immediate notification by the investigator to the Sponsor is required and documentation in the form of a case narrative. Such events may require further investigation to characterize and understand them. Refer to [Section 10.4](#), Appendix 4 for a list of AESIs pertinent to this study. All AESIs will be collected through the entire study period and must be reported to the Sponsor or designee immediately and in all circumstances within 24 hours of becoming aware of the event via the EDC system. If a site receives a report of a new AESI from a study participant or receives updated data on a previously reported AESI and the eCRF has been taken offline, then the site can report this information on a paper AESI form using the SAE Mailbox, the SAE Hotline, or the SAE Fax line ([Section 7.4.11](#)).

#### Acute Myocarditis and/or Pericarditis

All suspected cases of probable and confirmed myocarditis, pericarditis, or myopericarditis should be recorded as an AESI and reported as an SAE, if the event meets seriousness criteria. As an SAE, the event should be reported to the Sponsor or designee immediately and in all circumstances within 24 hours as per [Section 7.4.11](#). The investigator will submit any updated myocarditis, pericarditis or myopericarditis case data to the Sponsor within 24 hours of it being available. For reporting purposes, a participant who displays signs/symptoms consistent with the CDC case definition as described below ([Gargano et al, 2021](#)), should be reported as a potential case of confirmed or probable myocarditis, pericarditis, or myopericarditis.

#### Acute Myocarditis Case Definition

Presence of  $\geq 1$  new or worsening of the following clinical symptoms (persons who lack the listed symptoms but who meet other criteria may be classified as subclinical myocarditis [probable or confirmed]):

- Chest pain/pressure/discomfort

- Dyspnea/shortness of breath/pain with breathing
- Palpitations
- Syncope

OR

Infants and children aged < 12 years might instead have  $\geq 2$  of the following symptoms:

- Irritability
- Vomiting
- Poor feeding
- Tachypnea
- Lethargy

AND

For PROBABLE CASE:

Presence of  $\geq 1$  new finding of the following:

- Troponin level above upper limit of normal (any type of troponin)
- Abnormal electrocardiogram (ECG or EKG) or rhythm monitoring findings consistent with myocarditis
  - To meet the ECG or rhythm monitoring criterion, a probable case must include at least one of the following:
    - ST segment or T-wave abnormalities
    - Paroxysmal or sustained atrial, supraventricular, or ventricular arrhythmias
    - AV nodal conduction delays or intraventricular conduction defects
- Abnormal cardiac function or wall motion abnormalities on echocardiogram
- cMRI finding consistent with myocarditis ([Ferreira et al, 2018](#))

AND

- No other identifiable cause of the symptoms and findings

For CONFIRMED CASE:

- Histopathologic confirmation of myocarditis (using Dallas criteria [[Aretz, 1987](#)])

OR

- cMRI findings consistent with myocarditis in the presence of troponin level above upper limit of normal (any type of troponin)

AND

- No other identifiable cause of the symptoms and findings

### **Acute Pericarditis Case Definition**

Presence of  $\geq 2$  new or worsening of the following clinical features ([Adler, et al 2015](#)):

- Acute chest pain (Typically described as pain made worse by lying down, deep inspiration, or cough; and relieved by sitting up or leaning forward, although other types of chest pain may occur)
- Pericardial rub on examination
- New ST-elevation or PR-depression on EKG
- New or worsening pericardial effusion on echocardiogram or MRI

### **Myopericarditis Case Definition**

Participants who meet criteria for both myocarditis and pericarditis may be described under myopericarditis.

An independent Cardiac Event Adjudication Committee (CEAC) consisting of pediatric and adult cardiologists will review suspected cases of myocarditis, pericarditis, or myopericarditis to determine if they meet CDC criteria of “probable” or “confirmed” event, and to assess severity and enable the DSMB to make recommendations to the Sponsor to continue vaccine dosing. The CEAC will operate under the rules of an approved charter that will be written and reviewed at the organizational meeting of the CEAC. Details regarding the CEAC composition, responsibilities, procedures, and frequency of data review will be defined in its charter.

### **MIS-C Case Definition**

Investigators will also be asked to report, as an AESI, clinical signs/symptoms consistent with the CDC case definition of MIS-C ([CDC 2020d](#)):

- An individual aged  $< 21$  years presenting with fever, laboratory evidence of inflammation, and evidence of clinically severe illness requiring hospitalization, with multisystem ( $> 2$ ) organ involvement (cardiac, renal, respiratory, hematologic, gastrointestinal, dermatologic, or neurological)

AND

- No alternative plausible diagnoses

WITH OR WITHOUT

- Positive for current or recent SARS-CoV-2 infection by RT-PCR, serology (non-S protein-based), or antigen test or COVID-19 exposure within the 4 weeks prior to the onset of symptoms:
  - Fever  $\geq 38.0^{\circ}\text{C}/\geq 100.4^{\circ}\text{F}$  for  $\geq 24$  hours, or report of subjective fever lasting  $\geq 24$  hours
  - Including, but not limited to, one or more of the following: an elevated C-reactive protein, erythrocyte sedimentation rate, fibrinogen, procalcitonin, d-dimer, ferritin, lactic acid dehydrogenase, or interleukin 6; elevated neutrophils; reduced lymphocytes; or low albumin

Some participants may fulfill full or partial criteria for Kawasaki disease but it should be reported if they meet the case definition for MIS-C. Consider MIS-C in any pediatric death with evidence of SARS-CoV-2 infection.

#### **7.4.6 Recording and Follow-up of Pregnancy**

Female participants who have a positive pregnancy test at Screening should not be enrolled; participants who have a positive pregnancy test any time during the study should receive no further dosing with IP but should be asked to remain in the study and be monitored for safety.

Details of all pregnancies in female participants will be collected after the start of study treatment and until the end of their participation in the study.

- If a pregnancy is reported, the investigator should inform the Sponsor within 24 hours of learning of the pregnancy and should follow the procedures outlined in this section.
- Abnormal pregnancy outcomes (eg, spontaneous abortion, fetal death, stillbirth, congenital anomalies, ectopic pregnancy) are considered SAEs.

Pregnancies occurring in participants after enrollment must be reported to the Sponsor or designee within 24 hours of the study site learning of its occurrence, using the SAE Mailbox, the SAE Hotline, or the SAE Fax line ([Section 7.4.11](#)). If the participant agrees to submit this information, the pregnancy must be followed to determine the outcome, including spontaneous or voluntary termination, details of the birth, and the presence or absence of any birth defects, congenital abnormalities, or maternal and/or newborn complications. This follow-up should occur even if the intended duration of the safety follow-up for the study has ended. Pregnancy report forms will be distributed to the study site to be used for this purpose. The investigator

must immediately (within 24 hours of awareness) report to the Sponsor any pregnancy resulting in an abnormal outcome according to the procedures described for SAEs.

#### **7.4.7 Eliciting and Documenting Adverse Events**

The investigator is responsible for ensuring that all AEs and SAEs are recorded in the eCRF and reported to the Sponsor.

Solicited ARs will be collected from Day 1 through 7 days after each dose (ie, the day of injection and 6 subsequent days). Other (unsolicited) AEs will be collected from Day 1 through 28 days after each dose.

Both MAAEs and SAEs will be collected from participants as specified in the SoAs ([Section 10.1](#)) until the end of their participation in the study. Any AEs that occur before administration of IP will be analyzed separately from AEs that occur after vaccine administration.

At every study site visit or telephone contact, participants or parent(s)/LAR(s) will be asked a standard question to elicit any medically related changes in the participant's well-being (including COVID-19 symptoms). Participants or parent(s)/LAR(s) will also be asked if the participant has been hospitalized, had any accidents, used any new medications, changed concomitant medication regimens (both prescription and over-the-counter medications), or had any nonstudy vaccinations.

In addition to participant observations, physical examination findings or data relevant to participant safety classified as an AE will be documented on the AE page of the eCRF.

After the initial AE/SAE report, the investigator is required to proactively follow each participant at subsequent visits/contacts. All AEs and SAEs will be treated as medically appropriate and followed until resolution, stabilization, the event is otherwise explained, or the participant is LTFU (as defined in [Section 6.5](#)).

#### **7.4.8 Assessment of Intensity**

An event is defined as "serious" when it meets at least one of the predefined outcomes as described in the definition of an SAE ([Section 7.4.2](#)), NOT when it is rated as severe.

The severity (or intensity) of an AR or AE refers to the extent to which it affects the participant's daily activities. The Toxicity Grading Scale for Healthy Adult and Adolescent Volunteers Enrolled in Preventative Vaccine Clinical Trials ([DHHS 2007](#)), modified for use in children 37 months to < 12 years of age ([Table 8](#)) and 6 months to  $\leq$  36 months of age ([Table 9](#)), will be used to categorize local and systemic reactogenicity events (solicited ARs) and body temperature

measurements observed during this study. Specific criteria for local and systemic reactogenicity events are presented in [Section 7.4.3](#).

The determination of severity for all unsolicited AEs should be made by the investigator based upon medical judgment and the definitions of severity, as follows:

- Mild: These events do not interfere with the participant's daily activities.
- Moderate: These events cause some interference with the participant's daily activities and require limited or no medical intervention.
- Severe: These events prevent the participant's daily activity and require intensive therapeutic intervention.

Study staff should elicit from the participant or the parent(s)/LAR(s) the impact of AEs on the participant's activities of daily living to assess severity and document it appropriately in the participant's source documentation. Changes in the severity of an AE should be documented in the participant's source documentation to allow an assessment of the duration of the event at each level of intensity to be performed. An AE characterized as intermittent requires documentation of onset and the duration of each episode. An AE that fluctuates in severity during the course of the event is reported once in the eCRF at the highest severity observed.

#### **7.4.9 Assessment of Causality**

The investigator's assessment of an AE's relationship to IP is part of the documentation process but is not a factor in determining what is or is not reported in the study.

The investigator will assess causality (ie, whether there is a reasonable possibility that the IP caused the event) for all AEs and SAEs. The relationship will be characterized using the following classifications:

**Not related:** There is not a reasonable possibility of a relationship to the IP. Participant did not receive the IP OR the temporal sequence of AE onset relative to administration of the IP is not reasonable OR the AE is more likely explained by a cause other than the IP.

**Related:** There is a reasonable possibility of a relationship to the IP. There is evidence of exposure to the IP. The temporal sequence of AE onset relative to the administration of the IP is reasonable. The AE is more likely explained by the IP than by another cause.

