**Table 5: Pause Rule Criteria, Events, and Thresholds**

Pause Rule Criterion	Event	Participant Threshold for Triggering Study Pause
1	Any death due to SARS-CoV-2 infection	$\geq 1$
2	Any SAE or Grade 4 AE that cannot be reasonably attributed to a cause other than vaccination	$\geq 1$
3	ICU Admission due to COVID-19	$\geq 1$
4 	Individual Grade 3 or higher solicited local AR lasting $\geq 24$ hours and occurring within 7 days of injection (Days 1-7)	At least 2 participants and $\geq 5\%$ of the dosed participants in an age group
5 	Individual Grade 3 or higher solicited systemic AR lasting $\geq 24$ hours and occurring within 7 days of injection (Days 1-7)	At least 2 participants and $\geq 10\%$ of the enrolled participants in an age group
6 	Any $\geq$ Grade 3 or higher unsolicited AE that cannot be reasonably attributed to a cause other than vaccination	At least 2 participants and $\geq 5\%$ of the enrolled participants in an age group

Abbreviations: AE = adverse event; AR = adverse reaction; COVID-19 = coronavirus disease 2019; ICU = intensive care unit; SAE = serious adverse event; SARS-CoV-2 = severe acute respiratory syndrome coronavirus 2.

 “Individual AR” is defined as 1 AR type, eg, pain, erythema, or headache could each be an “individual AR.”

 Events in participants receiving booster doses will be considered separately from the events during the primary vaccination series.

If any of the thresholds for a study pause is met, the Sponsor will immediately suspend further enrollment and/or study dosing by notifying all investigators. Such a suspension will remain in force until the threshold events are reviewed by the DSMB and a recommendation to continue is provided to the Sponsor.

The investigator or designee is responsible for reporting to the Sponsor, via the electronic data capture (EDC) system, each event that potentially meets any pause rule criterion within 24 hours of observation. If an SAE assessed as related to IP by the investigator is reported at any point, the Sponsor’s medical monitor is responsible for a rapid assessment (with the Sponsor’s Medical and Safety team) of whether pause rule # 2 has been met; the Sponsor medical monitor may consult with the DSMB chair as an independent entity to make that determination, as described in the DSMB charter.

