### Events NOT Meeting the Adverse Event Definition

- Medical or surgical procedure (eg, endoscopy, appendectomy): the condition that leads to the procedure should be the AE.
- Situations in which an untoward medical occurrence did not occur (social and/or convenience admission to a hospital).
- Planned procedures (eg, tonsillectomy or pressure-equalization tubes) that occur during the study period but were planned prior to enrollment will not be considered AE unless complications arise.

An AR is any AE for which there is a reasonable possibility that the vaccine caused the AE ([Section 7.4.9](#)). For the purposes of IND safety reporting, “reasonable possibility” means that there is evidence to suggest a causal relationship between the vaccine and the AE.

An unsolicited AE is any AE reported by the participant that is not specified as a solicited AR in the protocol or is specified as a solicited AR but starts outside the protocol-defined period for reporting solicited ARs (ie, the day of each dose of injection and the 6 days after the day of dosing).

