**Table 11: Analysis Strategy for Safety Parameters**

Safety Endpoint	Number and Percentage of Participants, Number of Events	95% CI
Any solicited AR (overall and by local, systemic)	X	X
Any unsolicited AE	X	—
Any SAE	X	—
Any unsolicited MAAE	X	—
Any unsolicited treatment-related AE	X	—
Any treatment-related SAE	X	—
Discontinuation due to AE	X	—
Any severe AE	X	—
Any treatment-related severe AE	X	—

Abbreviations: AE = adverse event; AR = adverse reaction; CI = confidence interval; MAAE = medically attended adverse event; MedDRA = Medical Dictionary for Regulatory Activities; PT = preferred term; SAE = serious adverse event; SOC = system organ class.

Note: 95% CI using the Clopper-Pearson method. X = results will be provided. Solicited ARs and unsolicited AEs will be summarized by SOC and PT coded by MedDRA.

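### The Related and Not related categories in Section 7.4.9 use a balance-of-causes test that conflicts with the reasonable-possibility standard of 7.4.1, 7.4.11 and 7.4.9 itself, so the treatment-related rows of Table 11 can be understated

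*Protocol*

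**What the plan says.** Section 7.4.1 defines an adverse reaction: "An AR is any AE for which there is a reasonable possibility that the vaccine caused the AE". It refers the reader to 7.4.9 for the assessment. For IND safety reporting it adds that a reasonable possibility "means that there is evidence to suggest a causal relationship between the vaccine and the AE". Neither statement weighs the vaccine against other causes.

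Section 7.4.9 opens with the same question for every AE and SAE: "whether there is a reasonable possibility that the IP caused the event". Section 7.4.11 repeats it for SAEs. Section 7.4.9 then gives two answer categories.

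- *Not related* begins "There is not a reasonable possibility of a relationship to the IP". It goes on to list three grounds joined by OR: no IP received, unreasonable timing, or a likelier cause other than the IP.
- *Related* begins "There is a reasonable possibility of a relationship to the IP". It then lists exposure, reasonable timing and, last, "The AE is more likely explained by the IP than by another cause". No OR joins these elements.

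The call is used in three places.

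- Table 11 has rows for treatment-related unsolicited AEs, treatment-related severe AEs and "Any treatment-related SAE", each with participants, percentages and events.
- Section 6.2 cites 7.4.9 by number in one of its grounds for withholding further injections (an unsolicited AE of Grade 3 or above that the investigator considers related).
- Section 6.4 makes the call a prompt: "If an SAE assessed as related to IP by the investigator is reported at any point", the Sponsor's medical monitor must quickly assess whether pause rule 2 has been met.

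**The concern.** The investigator is asked one question and given answer categories that answer another. A reasonable possibility can exist while some other cause is as likely or likelier. The last sentence of *Related* removes such events from the category, although 7.4.1 calls them adverse reactions.

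Two investigators could classify the same SAE in opposite ways, each following the text. A statistical analysis plan cannot repair this, because the judgement is made and recorded at the site. The treatment-related rows also matter more where there is no placebo arm to compare with: Part 1 (about 1,275 participants) and Part 3 (about 300) are both open-label without one.

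**Working it through.** No arithmetic figure is at issue, so the check sets the passages side by side and asks whether the two categories are exhaustive and exclusive.

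**Standards in the protocol**

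| Place | Standard |
|---|---|
| 7.4.1, definition of an adverse reaction | Reasonable possibility |
| 7.4.9, opening question | Reasonable possibility |
| 7.4.11, SAE reporting | Reasonable possibility |
| 7.4.9, *Related*, last sentence | IP likelier than another cause |
| 7.4.9, *Not related*, last ground | Another cause likelier than the IP |
| Table 5, rule 2 | Own wording: no reasonable attribution to a cause other than vaccination |

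**Notation.** Let q be the weight of the IP as cause against all other causes, and r the level of q at which a reasonable possibility exists. The protocol gives no value for r. I assume r < 0.5, since evidence suggesting a causal link is less than a finding that the link is the likelier explanation.

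**Step 1.** Under 7.4.1 an event is an adverse reaction when q ≥ r.

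**Step 2.** Under 7.4.9, with the sentences of *Related* read together, an event is *Related* only when q > 0.5.

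**Step 3.** Events with r ≤ q ≤ 0.5 are therefore adverse reactions under 7.4.1 and not *Related* under 7.4.9.

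**Step 4.** Where these events go depends on how *Not related* is read.

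| Reading of *Not related* | r ≤ q < 0.5 | q = 0.5 |
|---|---|---|
| Opening sentence and one listed ground both needed | Neither category | Neither category |
| One listed ground is enough | *Not related*, despite a reasonable possibility | Neither category |

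Under both readings the tie has no category, and under both the whole band is lost from *Related*.

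**Step 5: what depends on the call.** Section 7.4.3 counts all solicited reactions as related, so they cannot move. Section 7.4.9 says causality does not decide what is reported, so total AE and SAE counts cannot move; AESIs are collected and reported whatever the cause. That leaves the treatment-related rows of Table 11 for unsolicited AEs, SAEs and severe AEs, the Grade 3 ground in 6.2, and the prompt in 6.4.

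**Step 6: direction.** Moving from q > 0.5 to q ≥ r with r < 0.5 can only add events to *Related*. The present wording can lower the related counts or leave them unchanged; it cannot raise them.

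**The case against.** The best defence is that the opening sentences of the two categories are exact complements and repeat the lead-in question. If they govern and the later sentences are only guidance, the categories are exhaustive and there is no gap. The protocol does not say this, and on that view the last sentence of *Related* has no effect. The inconsistency stands.

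The 7.4.1 explanation of a reasonable possibility is limited to IND safety reporting. That is correct, but the definition of an adverse reaction in the same section carries no such limit, so the conflict does not rest on the explanation.

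The defence is right about three larger consequences that a reader might infer.

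- *That pause rule 2 itself runs on the 7.4.9 scale.* It does not. Table 5 has its own attribution wording with a threshold of one participant. The *Related* call only prompts the medical monitor's assessment, and an event with a reasonable alternative cause might not meet rule 2 in any case. Investigators must separately report, within 24 hours, anything that might meet a pause criterion, and all SAEs reach the Sponsor within 24 hours regardless of causality.
- *That dosing decisions are blocked.* Section 6.2 is permissive. The same list allows withholding for an AE or SAE irrespective of causality, and for any AESI.
- *That rare events would be missed.* The primary safety endpoints are not filtered by relatedness. Suspected myocarditis and pericarditis are recorded as AESIs and adjudicated by an independent committee against case definitions.

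**Conclusion.** Section 7.4.9 contradicts 7.4.1, 7.4.11 and its own opening question, and its two categories do not cover every event. The effect is confined to unsolicited AEs and SAEs: the treatment-related rows of Table 11 can be understated, and the relatedness call in 6.2 and 6.4 is not applied on one scale.

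The size is not computable, because the protocol gives neither r nor the number of events in the affected band. The conclusion assumes r < 0.5 and that the sentences under *Related* are cumulative, as the absence of OR suggests. It is a classification fault worth correcting, not a failure of safety capture.

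**What to change.** In 7.4.9, delete the last sentence of *Related* and limit *Not related* to events with no reasonable possibility of a relationship to the IP. The categories are then exact complements and match 7.4.1 and 7.4.11. No default rule for unclassifiable events is needed, because none remain.

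State in the protocol how this standard relates to the separate attribution wording in Table 5, so that the two are reconciled for sites. The pause and dosing rules themselves stay as they are.

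The drafting cost is a few sentences and a site memo. Related counts may rise or stay the same. The larger cost comes from timing: at Amendment 9 many events have already been classified, so a change would leave two standards in one dataset. Events judged under the present text should be identified as such or re-reviewed. Section 7.4.10 lists the relationship call among the items collected but not the ground for it, so a re-review may not be able to single out the affected events from the recorded call alone.
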